4.2.7 Safety outcome variables

All safety variables will be summarised using the full analysis set (FAS) and data presented as a single group.

4.2.7.1 AI status

The number and percentage of patients with complete or indeterminate AI at the morning cortisol test will be tabulated along with the number and percentage with a result in the normal range. For those showing complete or partial/indeterminate AI, results of the subsequent ACTH stimulation tests and/or further morning cortisol tests will be tabulated so that pathways through the AI testing schematic can be evaluated. At DBL1, morning cortisol test and ACTH stimulation test results are presented for the initial morning cortisol test and repeat morning cortisol test; at DBL2, the additional tests at the end of OCS reduction phase and end of maintenance phase if applicable will also be summarised. Patients AI status (normal/partial AI/complete AI) at each stage will also be tabulated. Results will be repeated by baseline OCS dose and baseline duration of chronic OCS use.

A shift table will be presented for patients from their initial morning cortisol test to final AI status at the end of OCS reduction phase. A similar shift table will be presented for patients from their initial morning cortisol test to their final AI pathway status, including test results up to the end of the maintenance phase. Two additional shift tables will be presented which will include all available data at or after the protocol-defined initial morning cortisol test regardless of AI pathway compliance: the first showing AI status at the initial morning cortisol test vs. AI status at the additional test at the end of the maintenance phase; and the second showing AI status at the initial morning cortisol test vs. final AI status recorded ever in the study.

In addition, spaghetti plots will be produced for patients with partial AI (as determined by the ACTH stimulation test) following both the initial and repeat morning cortisol tests. The plots will show all available cortisol levels from the initial morning cortisol test, the repeat morning cortisol test and the end of the OCS reduction phase (if applicable). Morning cortisol test results and ACTH stimulation test results will be plotted side by side. Patients receiving oral oestrogen containing contraceptives will be plotted on separate pages. Similar plots for patients with partial AI at the initial morning cortisol test (ACTH stimulation test) and complete AI at the repeat morning cortisol test (\pm ACTH stimulation test) will also be produced. At DBL2, these graphic presentations will be repeated including all available cortisol data from the initial morning cortisol test, the repeat morning cortisol test, the end of the OCS reduction phase and the end of maintenance phase.

4.2.7.2 Adverse events

Adverse events will be summarised for the on-study period to end of OCS reduction phase at DBL1 and the overall on-study period at DBL2, as defined in Section 3.3.3. All AEs will be listed.

An overall summary table will be produced showing the number and percentage of patients with at least 1 AE in any of the following categories: AEs, deaths due to AE, serious AEs (SAEs), and AEs causing discontinuation of IP (DAEs). The total number of AEs in the different AE categories in terms of AE counts will also be presented (i.e. accounting for multiple occurrences of the same event in a patient).

Adverse events, DAEs and SAEs will be summarised by SOC and PT assigned to the event by MedDRA. For each PT, the number and percentage of patients reporting at least 1 occurrence will be presented, i.e. a patient with multiple occurrences of an AE will only be counted once. Serious AEs causing discontinuation of the study treatment and SAEs causing discontinuation from the study will also be summarised.

Adverse events and SAEs (by PT) will be summarised by Investigator's causality and maximum intensity. If a patient reports multiple occurrences of the same AE within the same reported period, the maximum intensity will be taken as the highest recorded maximum intensity (the order being mild, moderate, and severe). Deaths will also be summarised in separate tables.

A summary of the most common (i.e. frequency of $\geq 3\%$) AEs will also be presented.

Adverse events of injection site reactions (high level term of injection site reactions) will be summarised by PT for the on-study period. In addition, if there is a sufficient number of hypersensitivity events (standardised MedDRA query of hypersensitivity [narrow]), it will also be summarised by PT for the on-study period.

Separate listings of patients with AEs, SAEs, death due to AE, or discontinuations due to AEs will be presented.

4.2.7.3 Laboratory data

Laboratory parameters will be summarised as below for the on-study period to end of OCS reduction phase at DBL1 and the overall on-study period at DBL2, as defined in Section 3.3.3.

All continuous laboratory parameters will be summarised descriptively by absolute value at each visit, together with the corresponding changes from baseline. All parameters will be summarised in SI units, with the exception of cortisol results and blood eosinophil counts which will be summarised in both SI and conventional units. Results which are reported from the central laboratory in conventional units will be converted to SI units for reporting.

Central laboratory reference ranges will be used for the identification of abnormalities, and a shift table will be produced for each laboratory parameter to display low, normal, high, and

missing values. The shift tables will present baseline and maximum/minimum post-baseline value, as applicable for each parameter.

Shift plots showing each individual patient's laboratory value at baseline and at maximum/minimum post-baseline will be produced for each continuous laboratory variable. If any laboratory variables show any unusual features (high or low values or a general shift in the data points) at other time points then shift plots of these data may be produced.

Data for patients who have treatment-emergent changes outside central laboratory reference ranges will be presented. This data presentation will include all visits for this subset of patients.

Maximum post-baseline total bilirubin (TBL) elevations by maximum post-baseline ALT and AST will be presented, expressed as multiples of ULN. Bilirubin will be presented in multiples of the following ULN ≤ 1.5 , $>1.5-2$, >2 , and AST and ALT will be presented in multiples of the following ULN ≤ 1 , $>1-3$, $>3-5$, $>5-10$, >10 .

Maximum post-baseline TBL will be presented (<2 and ≥ 2 x ULN) and plotted against maximum post-baseline ALT (<3 , $\geq 3 - <5$, $\geq 5 - <10$, and ≥ 10 x ULN), expressed as multiples of ULN. This will be repeated to show maximum post-baseline TBL against maximum post-baseline AST.

Data for patients with ALT or AST ≥ 3 x ULN, and bilirubin ≥ 2 x ULN will be presented, which will include all visits for this subset of patients. A line plot of liver biochemistry test results (including ALP, ALT, AST, TBL and GGT) over time will also be presented for this subset of patients.

A shift table of HbA1c at baseline versus post-baseline will be produced to display normal ($<5.7\%$), pre-diabetes ($\geq 5.7\% - <6.5\%$), and diabetes ($\geq 6.5\%$).

Any data outside the central laboratory normal reference ranges will be explicitly noted on the listings that are produced.

4.2.7.4 Asthma exacerbations

The number of asthma exacerbations, number of patients with at least one exacerbation, number of exacerbations per patient, duration of exacerbation, number of exacerbations requiring hospitalization, number of exacerbations requiring emergency room visits, and number of exacerbations requiring OCS/Systemic Corticosteroid use will be summarised for the three study periods as defined in section 3.3.2. All asthma exacerbations will be listed by patient.

4.2.7.5 Glucocorticoid toxicity index

Glucocorticoid toxicity index and each of the 8 items will be summarised over time. Low density lipoprotein (LDL) > 3 mmol/L will be considered worsening. All recorded GTI data will be listed.

Statistical correlation between GTI and change in cumulative OCS dose at scheduled timepoints will be analysed graphically. The change in cumulative OCS dose would be calculated as:

(Total OCS dose from baseline to the visit) – (Total OCS had the patient remained on their baseline dose from baseline to the visit*)

* i.e. baseline daily OCS dose multiplied by the number of days from baseline to the visit

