### **5.2.7 Glucocorticoid toxicity index**

Glucocorticoid toxicity index will be assessed as described by [Miloslavsky et al 2017](#) (see Appendix [H](#) for details). The composite GTI captures common GC toxicities that are sensitive to differing cumulative GC doses over the period of a typical clinical trial (6 months to 3 years). The individual items within the GTI are weighted relative to each other for severity, and the instrument has the capability of measuring not only worsening of GC toxicity from baseline, but also improvement.

The composite GTI measures change in GC toxicity rather than absolute GC toxicity in order to account for the effects of prior GC therapy. Scoring should be performed as per the schedule of assessments, using entry assessment as the baseline. The GTI items were ranked in order of severity within each domain. The relative weights for each toxicity item were derived using multicriteria decision analysis. Multicriteria decision analysis has been used for

the creation of multiple classification criteria sets in a variety of inflammatory diseases, including rheumatoid arthritis ([Neogi et al 2010](#)), systemic sclerosis ([Johnson et al 2014](#)), and systemic lupus erythematosus ([Tedeschi et al 2018](#)).

The composite GTI will be assessed at the time points given in [Table 1](#). Only a subset of items from the composite GTI will be assessed in PONENTE: body mass index, glucose tolerance (glycosylated hemoglobin), BP, low-density lipoprotein, steroid myopathy, skin toxicity, neuropsychiatric toxicity, and infection (items from the Specific List will not be assessed).

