
 
a. Improvement in BP:                     
 
• Decrease in BP of >10% of baseline without medication increase, unless baseline systolic BP ≤ 120 and diastolic BP ≤ 85 OR
 
• Decrease in medication without an increase in BP of >10%, unless baseline systolic BP ≤ 120 and diastolic BP ≤ 85
 
 
 
b. No significant change in BP:                     
 
• BP within 10% of baseline or systolic BP ≤ 120 and diastolic BP ≤ 85 AND no change in medication OR
 
• Increase in either systolic or diastolic BP >10% with a decrease in medication OR
 
• Improvement in systolic or diastolic BP of > 10% with an increase in medication
 
 
 
c. Worsening of hypertension:                     
 
• Increase in BP of >10% such that the systolic BP exceeds 120 mmHg or the diastolic BP exceeds 85 mmHg without a change in medication OR
 
• An increase in anti-hypertensive medication accompanied by stability or no significant change in both the systolic and diastolic BP
 
 
 
d. Worsening of hypertension despite treatment:                     
 
• Increase in BP of >10% such that the systolic BP exceeds 120 mmHg or the diastolic BP exceeds 85 mmHg AND an increase in medication
 
 
 
	
4. Lipid metabolism (low-density lipoprotein [LDL] compared to baseline)	

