
 
a. Improvement in lipids:                     
 
• Decrease in LDL concentration >10% of baseline toward the target range without medication increase OR
 
• Decrease in medication without an increase in LDL of >10% or LDL remains within target range
 
 
 
b. No significant change in LDL:                     
 
• LDL within 10% of baseline or within the target range for patient AND no change in medication OR
 
• Increase in LDL > 10% with a decrease in medication OR
 
• Improvement in LDL of > 10% with an increase in medication
 
 
 
c. Worsening of LDL or medication status:                     
 
• Increase in LDL of >10% to above target range without a change in medication OR
 
• Increase in medication with <10% change in LDL
 
 
 
d. Worsening of LDL despite treatment:                     
 
• Increase in LDL of >10% AND an increase in medication
 
 
 
	
5. Bone Mineral Density (compared to baseline)	

 
a. Improvement – increase in BMD by >3%
 
b. No significant change (BMD between -3% and +3%)
 
c. Deterioration - decrease in BMD (BMD decrease by >3%)
 
	

% refers to total BMD in gms/cm^2
	
6. Glucocorticoid-induced myopathy	

 
a. No steroid myopathy
 
b. Mild steroid myopathy (weakness WITHOUT functional limitation)
 
c. Moderate steroid myopathy (weakness WITH functional limitation)
 
	

See Steroid Myopathy definitions, below
	
7. Skin	

 
a. No skin toxicity
 
b. Mild skin toxicity
 
c. Moderate skin toxicity
 
	

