	
by side. Plots will be repeated for patients with partial AI following the initial morning cortisol test and complete AI at the repeat. Patients taking oral estrogen containing contraceptive will be plotted on separate pages (section 4.2.7.1).
 
13. The threshold of LDL worsening for GTI calculation is defined (section 4.2.7.5).
 
14. The graphical analysis of statistical correlation between GTI and daily OCS dose is updated to be between GTI and change in cumulative OCS dose (section 4.2.7.5).
 
15. Appendix 8.2 is added to describe the analyses of COVID-19 impact.
 
16. Minor amendments to wording and grammar have been made throughout for improved clarity.

26 April, 2021	
Changes in line with Clinical Study Protocol amendments (to v4.0):
 
 1. Included the content of the PONENTE Long Term Follow Up Visit substudy and consequently, the following sections include a reference to the Addendum for the substudy: 
 • Section 1.2 – Study design • Section 2 – Analysis Sets • Section 3 – Primary and Secondary Variables • Section 4 – Analysis Methods 2. List of Abbreviations: Added the abbreviation for coronavirus disease 2019 (COVID-19). 3. Figure 1: Updated to include the long term follow up visit 12- to 18-months after end of PONENTE treatment period. Removed text regarding fixed-visits only related to benralizumab dosing; as this may be confusing in context of the long term follow up substudy. 4. Section 1.2- Study Design: 
 • Added new paragraph to describe the addition of a long term follow up period to the PONENTE study, high-level objectives, and to refer to an Addendum for details. An additional database lock for the substudy is also described. 5. Section 7 – List of References: Added new reference to GINA 2020 -this is the current GINA report at the start of the long term follow up substudy. 6. Added new appendix 8.3 - Additional reporting to assess the impact of the COVID-19 pandemic on data to the end of the study (DBL2). This section details the analyses of data impacted by COVID-19 pandemic at DBL2. 
Other changes:
 
 7. Section 2.2.1: To align with the updated Non-Compliance Handling Plan, the important protocol deviation of “failure to regularly record weekly

Date	Description of change

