3.3.6 Glucocorticoid toxicity index

Glucocorticoid toxicity index will be assessed as described by [Miloslavsky et al 2017](#) at the times detailed in the CSP. Only a subset of items from the composite GTI will be assessed in this study: BMI, glucose tolerance (glycosylated haemoglobin), BP, low density lipoprotein, steroid myopathy, skin toxicity, neuropsychiatric toxicity, and infection (items from the Specific List will not be assessed). Full details on GTI composite scoring are given in Appendix H to the CSP.

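### The SAP gives an absolute LDL cut-off of 3 mmol/L for GTI worsening without the change-from-baseline conditions of Appendix H, so as written it scores stable or falling LDL above 3 mmol/L as worsened.

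*SAP*

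**What the plan says.** SAP 4.2.7.5, on the GTI analysis, says that "Low density lipoprotein (LDL) > 3 mmol/L will be considered worsening". Nothing else in that section qualifies the statement. The amendment history entry of 1 September 2020 describes the addition this way: "The threshold of LDL worsening for GTI calculation is defined (section 4.2.7.5").

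SAP 3.3.6 leaves the scoring rule with the protocol: "Full details on GTI composite scoring are given in Appendix H to the CSP". Protocol 5.2.7 says that "The composite GTI measures change in GC toxicity rather than absolute GC toxicity in order to account for the effects of prior GC therapy", with scoring done "using entry assessment as the baseline".

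In Appendix H the lipid item has four categories, with these weights:

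- Improvement (-9): LDL falls by more than 10% towards target without a medication increase, or medication is reduced without a rise of more than 10% or with LDL still in target.
- No change (0): LDL stays within 10% of baseline or within the patient's target range with medication unchanged. Opposing moves of LDL and medication also fall here.
- Worsening (+10): a rise of more than 10% "to above target range without a change in medication", or a medication increase with less than 10% change in LDL.
- Worsening despite treatment (+30): a rise of more than 10% together with a medication increase.

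Appendix H gives no number for the target range and treats it as specific to the patient.

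**The concern.** The GTI is built as a change measure so that toxicity from earlier steroid use is not counted again. That matters here, because inclusion criterion 8 requires at least three months of chronic OCS before entry. An absolute LDL cut-off removes this protection for one item. A patient who enters with high LDL and stays there is scored as newly worsened, and so is a patient whose LDL falls but remains above 3 mmol/L.

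The GTI is the only outcome listed for the objective on corticosteroid toxicity after OCS reduction (protocol 2.3, SAP 1.1.3). The composite and each of its eight items are summarised over time, and the GTI is plotted against change in cumulative OCS dose. Points that reflect a patient's LDL level rather than its change would add scores unrelated to the OCS reduction and could hide real improvement.

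**Working it through.** The plan states no figure for the lipid item, so there is nothing to reproduce. The check scores the same LDL pairs under both rules.

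**Inputs.** The weights -9, 0, +10 and +30 and the Appendix H conditions are from the protocol. The cut-off of 3 mmol/L is from SAP 4.2.7.5 and also serves as the target limit when Appendix H is applied. Change = (follow-up - baseline) / baseline. The literal rule gives +10 whenever follow-up LDL exceeds 3 mmol/L.

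| LDL, mmol/L | Medication | Change | Literal SAP | Appendix H | Difference |
|---|---|---|---|---|---|
| 4.0 to 4.0 | unchanged | 0% | +10 | 0 | +10 |
| 4.0 to 3.8 | unchanged | -5% | +10 | 0 | +10 |
| 2.95 to 3.05 | unchanged | +3.4% | +10 | 0 | +10 |
| 4.0 to 3.2 | unchanged | -20% | +10 | -9 | +19 |
| 4.5 to 3.5 | unchanged | -22% | +10 | -9 | +19 |
| 2.6 to 3.2 | unchanged | +23% | +10 | +10 | 0 |
| 2.5 to 2.9 | unchanged | +16% | 0 | 0 | 0 |
| 2.6 to 3.2 | increased | +23% | +10 | +30 | -20 |
| 2.5 to 2.5 | increased | 0% | not flagged | +10 | -10 if scored 0 |

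For example, (3.5 - 4.5) / 4.5 = -22%, which Appendix H calls improvement; 10 - (-9) = 19.

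**If 3 mmol/L is only the target limit**, both rules coincide and every row takes its Appendix H score. No stable or improving patient is then misclassified.

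**Illustration of frequency.** The documents give no LDL distribution. The assumptions are: normal LDL with mean 2.5, 3.0 or 3.5 mmol/L, SD 0.9, no true shift, correlation between baseline and follow-up 0.7 or 0.9, and no medication change. Across these six settings:

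- the literal rule flags about 29% to 71% as worse, and Appendix H about 8% to 26%;
- about 15% to 56% are flagged without a rise of more than 10%;
- about 3% to 15% are flagged despite a fall of more than 10%.

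The mean excess in the lipid score is 10 x (share flagged without a rise of more than 10%) + 9 x (share flagged despite a fall of more than 10%). The lowest setting gives 10 x 0.145 + 9 x 0.041 = 1.8 points, and the highest gives 10 x 0.560 + 9 x 0.086 = 6.4 points. These figures leave out the downward errors in the last two table rows.

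**The case against.** The strongest reply is that the sentence was never meant to stand alone. Appendix H cannot be programmed without a number for the target range, and 3 mmol/L supplies one. SAP 3.3.6 still sends the reader to Appendix H for scoring, the amendment history speaks of a threshold rather than a new algorithm, and SAP section 6 lists no change to the lipid rule. On that reading the rise of more than 10% is still required.

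This is a fair reading, and it rules out a stronger one. A reader might infer that the SAP has replaced the Appendix H rule, or that it contradicts itself outright. The documents do not show that; a contradiction arises only when 4.2.7.5 is read in isolation.

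The reply does not remove the problem. The sentence mentions no target range, and the amendment entry ties the number to worsening. SAP 4.2.5.1 also asks for baseline LDL in GTI categories, although change categories cannot be scored at baseline; that makes an absolute cut-off a plausible programming outcome (an inference). Even on the kinder reading, one common limit replaces a patient-specific target without being declared, and the SAP does not say whether it also governs the improvement and no-change categories. Two programmers could follow this text and obtain different scores.

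It is also true that the consequence is limited. LDL is one of eight items in a descriptive safety index, the relation to OCS dose is examined only graphically, and LDL is summarised separately as a laboratory variable under SAP 4.2.7.3. A distorted item could be noticed and re-scored.

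**Conclusion.** The point holds as a defect in a stated rule whose intended meaning is uncertain. Followed as written, the sentence conflicts with protocol 5.2.7 and Appendix H. With unchanged medication and a 3 mmol/L target, it over-scores stable LDL above 3 mmol/L by 10 points and LDL that falls by more than 10% but stays above 3 mmol/L by 19. It under-scores some patients whose medication was increased, by 20 points in the example shown.

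A reader might infer that the GTI will be inflated by a known amount, or always upward. Neither is supported. The 1.8 to 6.4 points need both the literal reading and an assumed LDL distribution, and the errors with increased medication can run the other way.

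The effect stops at the lipid item, the GTI composite and the plot of GTI against change in cumulative OCS dose. The primary and secondary endpoints and the sample size are unaffected. The sentence should be corrected before GTI scores are derived.

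**What to change.** Replace the sentence in SAP 4.2.7.5 with wording such as: '3 mmol/L is used as the upper limit of the LDL target range. Improvement, no change, worsening and worsening despite treatment are scored by Appendix H, using change of more than 10% from baseline, relation to the target range, and medication change.' Apply it at every GTI time point after baseline. Add an entry to SAP section 6 stating that a common limit replaces the patient-specific target range of Appendix H.

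The cost is one sentence, one entry in section 6 and a check of the derivation. LDL and concomitant medication are already collected. The small downside is the loss of patient-specific targets, which the section 6 entry makes visible.

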4.2.7.6 Vital signs

Vital signs data will be summarised as below for the on-study period to end of OCS reduction phase at DBL1 and the overall on-study period at DBL2, as defined in section 3.3.3.

Descriptive statistics and change from baseline for vital signs data will be presented by visit. Baseline to maximum post-baseline and baseline to minimum post-baseline value shift tables will be generated, as applicable for each parameter and will include patients with both baseline and post-baseline data. All recorded vital signs data will be listed.

